## **6.4 Safety**

The Principal Investigator is responsible for ensuring that all staff involved in the study is familiar with the content of this section.

### **6.4.1 Definition of adverse events**

An adverse event (AE) is the development of an undesirable medical condition or the deterioration of a pre-existing medical condition following or during exposure to a pharmaceutical product, whether or not considered causally related to the product. An undesirable medical condition can be symptoms (eg, nausea, chest pain), signs (eg, tachycardia, enlarged liver) or the abnormal results of an investigation (eg, laboratory findings, electrocardiogram). In clinical studies, an AE can include an undesirable medical condition occurring at any time, including run-in or washout periods, even if no study treatment has been administered.

The term AE is used to include both serious and non-serious AEs.

Suspected cardiac ischaemic events including MI, severe recurrent cardiac ischaemia which lead to stent thrombosis and / or urgent revascularization should not be reported as AE/SAE (see section 6.4.5).

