- (g) Blood for Troponin (I or T) values need to be collected prior PCI, at 8, 16 and 24 hours post PCI.
- (h) Any AEs occurring after obtaining Informed Consent will be recorded until Visit 5. SAEs will be collected until Visit 6.
- (i) Any Endpoints occurring after obtaining Informed Consent will be recorded until the end of the 30 day study period.
- (j) All Medications will be recorded from the 7 days prior randomisation until Visit 5, or until V6 in case of new SAE/ endpoints.
- (k) The whole investigational products necessary for the study will be dispensed once, at Visit 1. The 1st dose of study medication will be given in pre-hospital settings. Date and time of the administration of the first loading dose will be recorded.
- (l) Date and time of the 2nd dose of Study medication will be recorded. This 2nd dose will be given in the Cath Lab, before ECG and initial angiography.
- (m) All patients will receive ticagrelor 90 mg twice daily (morning and evening, at approximately 12-hourly intervals) during 30 days.
- (n) Only applicable for open label extension enrolment
- (o) For prematurely discontinuation of study medication, suspected endpoints are collected until V6
- (p) *only applicable to patients participating in the sub-study presented in appendix D: PRIVATE-ATLANTIC Sub study (for details, please refer to section 5 and 6 of appendix D):*

For details of the visits, please refer to section 6.2

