## **5.9 Withdrawal from study**

Randomised patients are at any time free to withdraw from study (investigational product and assessments), without prejudice to further treatment. Investigators must explain to any such patient so requesting termination of their participation, the importance to the trial and to themselves of their continued participation by keeping study visits. Should the patient insist on not returning for visits, the investigators should attempt to arrange telephone or other acceptable contact at visit times so that adverse events and study endpoints can be assessed. Every effort must be made to collect outcome data on every patient, within the boundaries of each patient's right to privacy and local regulations.

Randomised patient who refuses to sign the full version of the Informed Consent Form before first dose intake of active maintenance ticagrelor 90 mg will be withdrawn from the study. The patient will be asked to document her/his withdrawal on the Informed Consent Form used in the ambulance and the investigator will document this in the patient's medical records. No further efficacy data will be collected from the time of documented refusal. For safety purpose, the patient will be followed by the investigator for a period of 7 days after the last loading dose intake.

If, after having signed the full Informed Consent Form, the patient wished to withdraw from study, this is documented by consent withdrawal on the consent withdrawal page of the Informed Consent Form. The appropriate option should be ticked, and the page signed and dated by both the patient and the investigator, if possible. Such patients will always be asked about the reason(s) and the presence of any adverse events. They will be seen and assessed by an investigator. Adverse events will be followed up (See Sections 6.4.3 and 6.4.4) and all study drugs should be returned by the patient.

Withdrawn patients will not be replaced.

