### **Visit 6: Safety Follow-up contact**

Completer patient will be contacted 7 days after the EOT visit. Any new SAEs will be recorded along with concomitant medication for SAE.

For patient who prematurely withdraws from study medication, a visit should occur at 30 days after randomisation and all suspected endpoints, procedures and new SAE (with its concomitant medications) should be collected. See section 5.8.3

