### **6.4.3 Recording of adverse events**

#### **Time period for collection of adverse events**

Non Serious Adverse Events will be collected from the time when informed consent is obtained until the end of the treatment period.

Serious Adverse Events will be collected from the time when informed consent is obtained until the end of the follow up period (maximum 30 plus 7 days).

AE/SAE collected in the Open Label Extension (OLE): After visit 6, for patients participating in the Open Label Extension phase, the Adverse Events/ Serious Adverse Events will be collected on a specific paper report form until 7 days after the end of the OLE treatment.

For patient who refused to sign full Informed Consent Form, the SAE will be collected from the last loading dose intake until the end of the 7 day follow up.

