#### **6.4.5 Reporting of suspected cardiac ischaemic events as adverse events**

Suspected cardiac ischaemic events should not be reported as AEs/SAEs. They are part of the natural history of the condition under investigation and therefore may be expected. All other events, with the exception of expected procedural-related bleeding events, will be reported as AEs/SAEs as detailed in Sections 6.4.3 and 6.4.4.

Once an event has been identified, using their clinical judgment, investigators must determine if the event could be classified as MI or recurrent cardiac ischaemia which lead to a stent thrombosis and/or an urgent revascularization.

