**Except in some clinical situations, suspected cardiac ischaemic events should not be reported as AEs/SAEs.**

Once a **suspected cardiac ischaemic** event has been identified, using their clinical judgment, investigators must determine if the event could be classified as MI or recurrent cardiac ischaemia which lead to a stent thrombosis and/or an urgent **coronary** revascularization.

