**Those will be recorded as endpoints and reported to the ICAC for central adjudication (see Section 6.3.2).**

All other **suspected cardiac ischaemic** events, **not meeting endpoint definitions**, will be reported as AEs/SAEs as detailed in Sections Sections 6.4.3 and 6.4.4.

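### MI and stent-related ischaemic events are exempt from AE/SAE reporting with no end date, so non-fatal events have no consistent recording route after refusal of full consent or between day 30 and Visit 6

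*Protocol*

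**What the plan says.** **The exemption.** Section 6.4.1 states that suspected cardiac ischaemic events, MI among them, and "severe recurrent cardiac ischaemia which lead to stent thrombosis and / or urgent revascularization should not be reported as AE/SAE". The body text of 6.4.5 gives the same rule and a reason: "Suspected cardiac ischaemic events should not be reported as AEs/SAEs. They are part of the natural history of the condition under investigation". Administrative Change 4 revises 6.4.5 to read "Except in some clinical situations, suspected cardiac ischaemic events should not be reported as AEs/SAEs". It then has the investigator judge whether the event is an MI, or ischaemia leading to stent thrombosis or urgent coronary revascularization. Of events so classified it says "Those will be recorded as endpoints and reported to the ICAC for central adjudication (see Section 6.3.2"). Only suspected ischaemic events that fall outside the endpoint definitions go to AE/SAE reporting. None of these texts gives a study day.

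**The endpoint route.** Table 1 note (i): "Any Endpoints occurring after obtaining Informed Consent will be recorded until the end of the 30 day study period". Note (o) extends collection to Visit 6 for patients who stop study medication early. Section 12.4 gives the adjudication committee a 30-day remit. After refusal of full consent, section 5.9 says "No further efficacy data will be collected from the time of documented refusal".

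**The SAE route.** Section 6.4.3 collects SAEs to the end of follow-up, at most 30 plus 7 days. For refusers it collects them for 7 days after the last loading dose. For completers, the Visit 6 text in 6.2.1 says "Any new SAEs will be recorded along with concomitant medication for SAE" and does not mention endpoints. For the extension, 6.4.3 says "After visit 6, for patients participating in the Open Label Extension phase, the Adverse Events/ Serious Adverse Events will be collected", on a separate paper form. Section 8.4 says that no further data are gathered once a patient declines to complete consent.

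**The concern.** Leaving an event out of AE/SAE reporting is sound while the same event is captured and adjudicated as an endpoint. Once endpoint collection closes for a patient and SAE collection continues, the exemption removes the only route left. The events concerned are MI, stent thrombosis and ischaemia-driven revascularization, in patients who have recently been stented.

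At stake is the completeness of safety data in those windows and what reaches the sponsor's safety reporting. A site that follows one section may break another, and sites may resolve the conflict differently.

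**Working it through.** The protocol states no figure on this point. The check sets the collection periods side by side for each patient group and then sizes the result.

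**Step 1: does a late event still meet the endpoint definition?** The definitions in 6.3.2 of MI, urgent revascularization and definite stent thrombosis carry no study-day limit. Judged against 6.3.2, to which revised 6.4.5 refers, an MI on day 33 meets the definition and stays outside the AE/SAE branch.

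**Step 2: compare the routes.**

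| Group and window | Endpoint route | SAE route | Non-fatal MI or stent thrombosis |
|---|---|---|---|
| Consenting patient, to day 30 | Open | Exempt | Covered as endpoint |
| Stops drug by day 23; Visit 6 on days 28 to 32 (5.8.3) | Open to Visit 6 | Exempt | Covered |
| Stops drug on days 24 to 27; Visit 6 seven days later, so days 31 to 34 (5.8.3) | Open to Visit 6 | Exempt | Covered |
| Refuses full consent, to 7 days after last loading dose | Closed by 5.9 | Collected under 5.9 and 6.4.3, denied by 8.4, exempt under 6.4.1 | No route |
| Completer, day 30 to Visit 6 | Closed by Table 1 note (i) and 12.4; left undated by revised 6.4.5 | Collected, but exempt under 6.4.1 | Conflicting instructions |
| Extension, after Visit 6 | None described | Paper form, but exempt under 6.4.1 | No clear route; after the 30+7-day period |

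Fatal events have a route in every row, because 6.3.2.6 has a known cause of death reported as the SAE.

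**Step 3: size in completers.** The inputs are the 12-month rates on ticagrelor in the PLATO STE-ACS table in section 1.1.2.2 (MI 4.7%, definite stent thrombosis 1.6%) and 1770 randomised patients. The assumptions are that all complete and that the hazard is constant over the year.

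- MI over 7 days: 4.7% × 7/365 = 0.090%; × 1770 = about 1.6 patients.
- Definite stent thrombosis over 7 days: 1.6% × 7/365 = 0.031%; × 1770 = about 0.5 patients, overlapping with MI.
- Range: Visit 5 may fall on days 28 to 32 and Visit 6 is 7 days later, on days 35 to 39. The window after day 30 is then 5 to 9 days. With 1770 × 4.7% = 83.2, this gives 83.2 × 5/365 = 1.1 to 83.2 × 9/365 = 2.1 MIs.

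**Step 4: size elsewhere.** The number of refusers is not given. At the same constant hazard, 7 days carries 0.090% per refuser, or 0.09 MIs per 100. That figure is too low if risk in the week after the index event exceeds the yearly average. The number of extension patients is not given either. One followed from day 30 to month 12 would carry 4.7% × 335/365 = 4.3%, part of which falls before Visit 6.

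**Separate minor point.** Table 1 note (n) places extension enrolment at Visit 5. Non-serious AEs stop at Visit 5 (note h) and resume after Visit 6 (6.4.3). A patient continuing the drug has about 7 days without non-serious AE recording; SAEs are still collected.

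**The case against.** The strongest reply is that the text can be read so that late events do have a route, and there are two such readings.

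- Revised 6.4.5 sends these events to the endpoint forms and the adjudication committee without a date, so a day-33 MI could be entered there.
- The abbreviations list defines an endpoint as a centrally adjudicated event specified as an efficacy variable. The clinical efficacy variables cover 30 days, so an MI after day 30 would not be an endpoint and would fall to the AE/SAE branch.

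The opening exception in revised 6.4.5, the eCRF instructions and the endpoint manual, which are not shown, may also settle the routing.

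This stands in part. It rules out the stronger claim a reader might draw, that these events are recorded nowhere. But the two readings give opposite instructions for the same day-33 event, and the first conflicts with Table 1 note (i) and section 12.4. The only exception that revised 6.4.5 goes on to describe is for events outside the endpoint definitions. Neither reading helps the refuser: the event falls in the first week, inside the 30 days, where 5.9 closes the endpoint route and 6.4.1 the SAE route.

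The reply is also right on impact. Both arms take the same open-label ticagrelor after the loading doses, so nothing suggests that losses would differ by arm. The co-primaries are measured before PCI, and the 30-day secondary and safety objectives end before the completer window opens.

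**Conclusion.** The concern holds in limited form. The exemption has no end date, endpoint collection is shorter than SAE collection, and non-fatal MI, stent thrombosis and ischaemia leading to urgent revascularization have no consistent route in two windows. The refuser window is the firmer: 5.9 and 6.4.1 close both routes, and 8.4 contradicts the safety follow-up itself. The completer window is a conflict between revised 6.4.5 and Table 1 note (i) with the 30-day adjudication period. The extension inherits the same wording, but it should not be counted as a third on-study window because it follows the 30+7-day study period.

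The expected size in completers is small: about 1.6 MIs (1.1 to 2.1 over the visit window), if all 1770 complete and the hazard is constant. It cannot be sized for refusers or the extension, whose numbers are not given.

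A reader might infer that the trial's safety conclusions would be falsely reassuring. The documents do not support that: no planned analysis draws an ischaemic safety conclusion from these windows, and the primary and 30-day secondary analyses in consenting patients are unaffected. This is a low-to-moderate correction to safety reporting, not a condition for the trial to proceed.

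**What to change.** - In 6.4.1 and 6.4.5, limit the exemption to the period in which endpoints are being collected for that patient: to day 30, or to Visit 6 for those who stop study medication early.
- State that an MI, stent thrombosis or ischaemia-driven revascularization meeting SAE criteria is reported as an SAE if it occurs after that period, after refusal of full consent, or in the extension.
- Reconcile 5.9, 6.4.3 and 8.4 on what is collected after refusal, and bring Table 1 notes (i) and (o) into line with revised 6.4.5.
- In 6.4.3, start extension AE collection at Visit 5, which closes the separate gap in non-serious AEs.

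The cost is wording in these sections and the eCRF instructions, plus a small number of extra SAE reports. No visit is added, and no treatment rule or planned analysis changes.

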### **6.4.2 Definitions of serious adverse event**

A serious adverse event is an AE occurring during any study phase (ie, run-in, treatment, washout, follow-up), that fulfils one or more of the following criteria:

Results in death

Is immediately life-threatening

Requires in-patient hospitalisation or prolongation of existing hospitalisation

Results in persistent or significant disability or incapacity

Is a congenital abnormality or birth defect

Is an important medical event that may jeopardise the patient or may require medical intervention to prevent one of the outcomes listed above.

For further guidance on the definition of a SAE, see Appendix B to the Clinical Study Protocol.

### **6.4.3 Recording of adverse events**

#### **Time period for collection of adverse events**

Non Serious Adverse Events will be collected from the time when informed consent is obtained until the end of the treatment period.

Serious Adverse Events will be collected from the time when informed consent is obtained until the end of the follow up period (maximum 30 plus 7 days).

AE/SAE collected in the Open Label Extension (OLE): After visit 6, for patients participating in the Open Label Extension phase, the Adverse Events/ Serious Adverse Events will be collected on a specific paper report form until 7 days after the end of the OLE treatment.

For patient who refused to sign full Informed Consent Form, the SAE will be collected from the last loading dose intake until the end of the 7 day follow up.

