10.	TIMI flow grade 3 at end of procedure.	TIMI flow grade 3 at end of procedure

Safety objectives	Outcome variables

1. To assess the safety of pre-hospital vs. in-hospital initiation of ticagrelor therapy using PLATO bleeding definition, within the first 48 hours and during 30 days of study
	
Bleeding events
 
(a) The total number of patients with major life-threatening bleeding events
 
(b) Total number of patients with other major bleeding events,
 
(c) Total number of patients with minor or major bleeding events
 
The above endpoints will be defined according to PLATO bleeding definition (excluded CABG-related bleeding), within the first 48 hours and, , during 30 days of study defined as follows:
 
 
– major life-threatening bleeding: fatal bleeding, intracranial bleeding, intrapericardial bleeding with cardiac tamponade, hypovolemic shock or severe hypotension due to bleeding and requiring vasopressors or surgery, decline in the hemoglobin concentration of 5.0 g/dL or more, or need for transfusion of at least 4 units of red cells,
 
– other major bleeding: bleeding that led to clinically significant disability (e.g., intraocular bleeding with permanent vision loss) or bleeding associated with a drop in the haemoglobin concentration of at least 3.0 g/dL but less than 5.0 g/dL or requiring transfusion of 2 to 3 units of red cells,
 
– minor bleeding: any bleeding requiring medical intervention but not meeting the criteria for major bleeding.
 

2. To assess the safety of pre-hospital vs. in-hospital initiation of ticagrelor therapy in term of adverse events within 30 days of study
	
Other safety events
 
Adverse events, abnormal laboratory findings, physical examination, vital signs within 30 days of study

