## **2.3 Safety objective**

Bleeding events:

To assess the occurrence of non CABG related bleedings major life-threatening bleeding events, other major bleeding events and minor or major bleeding events in pre-hospital vs. in-hospital initiation of ticagrelor therapy according to PLATO bleeding definition, (see section 6.4.6.1), within the first 48 hours and during 30 days of study .

Other safety events:

To assess the occurrence of any other adverse events in pre-hospital vs. in-hospital initiation of ticagrelor therapy within 30 days of study

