### **5.8.3 Procedures for discontinuation of a patient from investigational product**

The patient once randomised is in the study for 30 days. If the patient is permanently discontinued from study medication, the patient should do the End of Treatment visit (V5). A follow-up contact (Visit 6) should be performed in order to collect all AEs/SAEs and suspected endpoints at 30 days post randomisation or 7 days after treatment.

A patient that decides to discontinue investigational product will always be asked about the reason(s) and the presence of any adverse events. If possible, they will be seen and assessed by an investigator(s). Adverse events will be followed up (See Sections 6.4.3 and 6.4.4); and all study drugs should be returned by the patient.

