#### **For premature discontinuation from study medication:**

If premature discontinuation occurs at  $\leq 23$  days (Visit 5), then Visit 6 should be done between 28 and 32 days with SAE and suspected endpoints collected at that visit.

If premature discontinuation occurs between 24 and 27 days (Visit 5), then Visit 6 should be done 7 days following Visit 5 with SAE and suspected endpoints collected at that visit.

If a patient is withdrawn from study, see Section 5.9.

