### **Visit 5: End of Treatment visit (EOT)**

This visit should take place at the end of the planned treatment period (30 days) or if the patient discontinues prematurely from the study treatment.

Suspected endpoint events, AE/SAE and current medications will be recorded. For patients reporting suspected endpoint events, SAEs, discontinuing study medication due to an AE, all peri-event medications will be recorded.

All remaining study medication will be returned and drug accountability performed.

The following assessments will be performed: see Visit 4.

After this 30 day period, it is up to the investigator to decide whether the patient should be maintained on ticagrelor as a component of dual antiplatelet therapy or continued antithrombotic therapy.

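### For patients who stop study drug early, the protocol gives Visit 6 two conflicting contents, and under the narrower one new non-serious adverse events go unrecorded for the rest of the 30 days

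*Protocol*

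**What the plan says.** The window for the outcome is fixed in two places. Section 2.3 gives the objective as "To assess the occurrence of any other adverse events in pre-hospital vs. in-hospital initiation of ticagrelor therapy within 30 days of study", and the synopsis lists the outcome variable as "Adverse events, abnormal laboratory findings, physical examination, vital signs within 30 days of study".

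The collection rules are these:

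- Section 6.4.3: "Non Serious Adverse Events will be collected from the time when informed consent is obtained until the end of the treatment period".
- Table 1, note (h): "Any AEs occurring after obtaining Informed Consent will be recorded until Visit 5. SAEs will be collected until Visit 6". The adverse-event row of the table is marked at Visits 1 to 5 and not at Visit 6. The serious-event row is marked at all six.
- Section 6.2.1, Visit 5: the visit takes place at the end of the planned 30 days "or if the patient discontinues prematurely from the study treatment". The abbreviation list likewise defines end of treatment as the visit at which study medication is discontinued.
- Section 5.8.3, opening paragraph: after a permanent discontinuation, Visit 6 "should be performed in order to collect all AEs/SAEs and suspected endpoints at 30 days post randomisation or 7 days after treatment". The same paragraph keeps the randomised patient in the study for 30 days.
- Section 5.8.3, rules for premature discontinuation: if the stop is on day 23 or earlier, "then Visit 6 should be done between 28 and 32 days with SAE and suspected endpoints collected at that visit". For stops on days 24 to 27, Visit 6 comes 7 days after Visit 5, with the same limited content.
- Section 6.2.1, Visit 6: for early stoppers it lists suspected endpoints, procedures and new serious events.

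**The concern.** One section gives two contents for the same visit. A site that follows the opening of 5.8.3 records non-serious events at Visit 6. A site that follows the specific rules, Table 1 or the Visit 6 description does not. The data could then differ between sites because of how the text was read.

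Under the narrower reading, the stated outcome and its collection do not match. The outcome runs to 30 days of study, but in an early stopper the non-serious part of it is observed only up to the stop. Section 12.2.4 plans adverse-event summaries by arm and more detailed analyses of dyspnoea and bradycardic events, some of which may be non-serious. Section 5.8.2 names ventricular pauses and syncope related to bradycardia among its example reasons for permanent discontinuation, so follow-up can be shortened by the kind of event under study. An analysis plan cannot repair this, because events never entered in the eCRF cannot be recovered at analysis.

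**Working it through.** The protocol gives no figure to reproduce here. The check sets the passages side by side, and the only arithmetic is on days.

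**Step 1. When does Visit 5 fall for an early stopper?** Section 6.2.1 (Visit 5), section 5.8.3 and the abbreviation list all place it at discontinuation. So for a stop on day d, Visit 5 is on about day d.

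**Step 2. What is collected after Visit 5 in these patients?**

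| Source | Non-serious AEs | Serious AEs | Suspected endpoints |
|---|---|---|---|
| 5.8.3, opening paragraph | yes | yes | yes |
| 5.8.3, premature-discontinuation rules | not listed | yes | yes |
| 6.2.1, Visit 6 | not listed | yes | yes (and procedures) |
| Table 1, rows and notes (h), (o) | end at Visit 5 | to Visit 6 | to Visit 6 |
| 6.4.3 | end with treatment period | to end of follow-up | not addressed |

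The first row conflicts with the next three. The last row agrees with them once note (h) is used to date the end of the treatment period.

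**Step 3. How much of the window is uncovered under the narrower rule?** Days without recording of new non-serious events = 30 - d.

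- d = 1: 30 - 1 = 29 days
- d = 15: 30 - 15 = 15 days
- d = 23: 30 - 23 = 7 days
- d = 24: 30 - 24 = 6 days
- d = 27: 30 - 27 = 3 days

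**Step 4. Is there already a contact at which these events could be recorded?** For d up to 23, Visit 6 falls on days 28 to 32. For d from 24 to 27 it falls 7 days after Visit 5, which is 24 + 7 = day 31 to 27 + 7 = day 34. A contact near or after day 30 therefore exists in every case. Only its content is in dispute.

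**Step 5. Does a later change settle it?** Administrative Change 4 replaces the instruction in 5.8.2 to keep all visits with follow-up according to 5.8.3. That sends the reader to the section that contradicts itself and does not choose between its two statements.

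**The case against.** The sentence in 6.4.3 need not be wrong by itself. The end of the treatment period could mean the planned period, since Table 1 labels a 30-day active treatment period and the Visit 5 text refers to a planned one. Read that way, 6.4.3 agrees with the objective and with the opening of 5.8.3. This is fair to 6.4.3 alone, but note (h) ties the end of recording to Visit 5, and Visit 5 is held at discontinuation. The conflict among 5.8.3, Table 1 and the Visit 6 text remains.

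Collecting non-serious events only on treatment is also a legitimate choice. Section 5.6.9 says the platelet effect has largely gone by 48 to 72 hours after stopping. That stands, and it is why restating the outcome would be an acceptable remedy. The protocol has not made that choice, because its outcome runs over 30 days of study.

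Several stronger readings are tempting, and the documents do not support them:

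- **That the whole 30-day safety outcome is lost in early stoppers.** Serious events run to Visit 6, and so do suspected endpoints in these patients. Bleeds are treated as suspected safety endpoints in 6.4.6, have their own eCRF record, and are adjudicated over the 30 days (12.4), apart from minimal bleeds (6.4.6.3), which are not among the bleeding outcomes.
- **That the dyspnoea and bradycardia counts lose the event that caused the stop.** That event precedes Visit 5 and is recorded there. In a per-patient count the patient is already a case. What may be missed is a different, later, non-serious event.
- **That the comparison between arms is biased.** Both arms take the same maintenance regimen and differ only in when the loading dose is given. Nothing in the protocol points to different rates of stopping. Bias would arise only if the rates differed, and would then make the arm with more early stops look safer. The planned summaries are descriptive.
- **That Visit 6 comes too early after a stop on day 22 or 23.** At the early edge of the window the gap is 28 - 22 = 6 or 28 - 23 = 5 days. But 5.8.3 offers day 30 or 7 days after treatment as alternatives, and a nominal day-30 visit after a day-23 stop gives 30 - 23 = 7 days. This is visit-window tolerance and not a contradiction.

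**Conclusion.** The point holds as a conflict of wording with a bounded consequence. Section 5.8.3 gives two contents for Visit 6 in early stoppers, and Table 1 with note (h) and the Visit 6 description side with the narrower one. If the narrower one is followed, new non-serious adverse events are unrecorded for about 30 - d days after a stop on day d, although the stated outcome covers 30 days of study. If the opening of 5.8.3 is followed, there is no gap, but the other passages are then wrong.

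The loss concerns new non-serious events after discontinuation only. A reader might want to express it as a share of observation time or of patients. The protocol states no rate or timing of early discontinuation, so any such figure would rest entirely on assumed inputs, and none is given here. Confidence is high for the textual conflict. Any effect on the comparison between arms is conditional and cannot be quantified from the documents.

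The point should be corrected because sites cannot follow both rules and events that were not collected cannot be recovered.

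**What to change.** Make one of two choices and carry it through every place.

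1. **Keep the 30-day outcome.** Align the premature-discontinuation rules of 5.8.3, the Visit 6 description in 6.2.1, the Table 1 adverse-event row and note (h), and section 6.4.3 with the opening paragraph of 5.8.3. For patients who stop early but remain in the study, non-serious events up to day 30 are then recorded at the Visit 6 they already have. The cost is a wording change, the adverse-event form opened at an existing contact, and a few more entries. No extra visit is needed and the timing of Visit 6 need not change.

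2. **Keep on-treatment collection.** Restate the objective in 2.3 and the synopsis outcome so that non-serious events are covered only to the end of treatment, and remove non-serious events from the opening sentence of 5.8.3 on Visit 6. This costs only wording, but it gives up the 30-day view of non-serious events in early stoppers.

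The first choice preserves the outcome as the protocol now states it.
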